4.4.2 Male Contraception

Contraception is required for all sexually-active male subjects and their partners. All male subjects (including those who are sterile) agree not to donate sperm, and to use 1 of the following

approved methods of contraception from the baseline visit on Day 0 until 30 days following study discharge:

- Male condom with spermicide
- Sterile sexual partner
- Intrauterine device with spermicide (use by female sexual partner)
- Female condom with spermicide (use by female sexual partner)
- Contraceptive sponge with spermicide (use by female sexual partner)
- Intravaginal system (eg, vaginal ring with spermicide, a diaphragm with spermicide, or a cervical cap with spermicide) (use by female sexual partner)
- Oral, implantable, transdermal, or injectable hormonal contraceptive (use by female sexual partner) plus a barrier method

4.5 Discontinuation of Subjects

A subject may withdraw from the study at any time for any reason without prejudice to their future medical care by the physician or at the institution. The investigator or sponsor may withdraw the subject at any time (eg, in the interest of subject safety). The investigator is encouraged to discuss withdrawal of a subject from the IP with the CRO Medical Monitor when possible.

If the IP is discontinued, regardless of the reason, the evaluations listed for both Visit 9/end of study (EOS) and Visit 10/Follow-up, are to be performed as completely as possible; however, the EOS liver biopsy will not be required for patients discontinuing prior to Week 44.

Comments (spontaneous or elicited) or complaints made by the subject must be recorded in the source documents. The reason for termination, date of stopping the IP, and the total amount of the IP taken must be recorded in the electronic case report form (eCRF) and source documents.

Subjects who discontinue will not be replaced.

4.5.1 Subject Withdrawal Criteria

Medically important events that in the opinion of the investigator, medical monitor or sponsor would compromise the subject's ability to safely continue in the study may result in withdrawal of the subject from the study. Subjects who become pregnant or demonstrate disease progression, defined as the development of signs or symptoms of hepatic decompensation (ie, esophageal variceal hemorrhage, hepatic encephalopathy, ascites, or hepatocellular carcinoma), will be withdrawn from the study and followed as set forth in the protocol.

4.5.2 Reasons for Discontinuation

The reason for withdrawal must be determined by the investigator and recorded in the subject's medical record and on the eCRF. If a subject is withdrawn for more than 1 reason, each reason

should be documented in the source document and the most clinically relevant reason should be entered on the eCRF.

Reasons for discontinuation include but are not limited to:

- Adverse event (AE)
- Protocol violation
- Withdrawal by subject
- Lost to follow-up
- Lack of efficacy
- Death
- Screen failure
- Noncompliance with study drug
- Physician decision
- Pregnancy
- Progressive disease (refer to Section 4.5.1)
- Study terminated by sponsor
- Other - If “Other” is selected, the investigator must specify the reason on the eCRF

4.5.3 Subjects Lost to Follow-up Prior to Last Scheduled Visit

A minimum of 3 documented attempts must be made to contact any subject lost to follow-up at any time point prior to the last scheduled contact clinic visit. At least 1 of these documented attempts must include a written communication sent to the subject’s last known address via courier or mail (with an acknowledgement of receipt request) asking that they return to the site for final safety evaluations and return any unused IP.

4.5.4 Safety-related Stopping Rules

Refer to [Appendix 4](#) and [Appendix 5](#) for criteria to assess severity of liver-related AEs and stopping rules for liver-related blood tests, respectively.

An urgent safety review will be conducted within 7 days by the sponsor and in consultation with the DMC if 1 or more of the following criteria are met:

- Death that is considered related to the study drug
- Two SAEs of similar type (defined as same or similar Medical Dictionary for Regulatory Activities (MedDRA) higher level group code), and considered related to the study drug.

The urgent review will be performed by a sponsor safety review group, which will include the study Global Safety Lead (GSL) and the Global Drug Safety (GDS) therapeutic area (TA) Head,

and in consultation with the DMC. The GDS TA Head, not the GSL involved in the study, may be unblinded as part of this urgent safety review, if required. Following the sponsor's review of safety data and consultation with the DMC, one of the following actions will be taken with respect to study status:

- Continue study with protocol unchanged
- Continue study with modifications to the protocol
- Terminate study

Subject safety will be monitored on a continuous basis during this study until the last subject completes his or her last scheduled study visit/assessment.

5 PRIOR AND CONCOMITANT TREATMENT

All non-study treatment (including but not limited to herbal treatments, vitamins, behavioral treatment, non-pharmacological treatment, such as psychotherapy, as appropriate) received within 30 days prior to signing informed consent at the screening visit (Visit 1) and through the final study contact (including protocol-defined follow-up period) must be recorded on the appropriate eCRF page.

5.1 Prior Treatment

Prior treatment includes all treatment (including but not limited to herbal treatments, vitamins, and behavioral treatment, non-pharmacological treatment, such as psychotherapy, as appropriate), received within 30 days of the date of first dose of the IP. Prior treatment information must be recorded on the appropriate eCRF page.

5.2 Concomitant Treatment

Concomitant treatment refers to all treatment taken between the dates of the first dose of the IP and the end of the follow-up period, inclusive. Concomitant treatment information must be recorded on the appropriate eCRF page.

5.2.1 Permitted Treatment

Medications and supplements including but not limited to vitamin E, betaine, s-adenosyl-l-methionine, ursodeoxycholic acid, milk thistle, gemfibrozil, anti-TNF therapies, probiotics biguanides (metformin), thiazolidinediones (TZDs) and GLP-1 RAs that have been used to treat NAFLD/NASH are allowed during the course of the study if the subject has been on a stable dosing regimen (ie, same dose and frequency in the previous 6 months prior to the qualifying liver biopsy and not initiated after qualifying liver biopsy) and will continue this dosing regimen throughout study participation. Use of antiplatelet medications is also allowed. The investigator must contact the CRO medical monitor to discuss any changes to concomitant medications that may impact the study.

5.2.2 Prohibited Treatment

The following list of prohibited drugs cannot have been taken for more than 2 weeks within the 6 months prior to randomization and are excluded while on study.

- Systemic Glucocorticoids
- Tamoxifen
- Amiodarone
- Methotrexate
- Alcohol (see Section 4.2)
- Griseofulvin
- Total parenteral nutrition
- Obeticholic acid
- Valproate
- Nucleoside Analogues (except acyclovir)
- Tetracycline (high dose; >1g)
- Estrogens at doses greater than 2 mg QD used for hormone replacement
- Anabolic steroids
- Bile acid sequestrants such as cholestyramine or colestipol
- Any other known hepatotoxins including over-the counter therapies and herbal therapies such as germander, chaparral and ma-huang.

This is not a comprehensive list. Treatments not listed above are generally considered allowable, unless considered a potential hepatotoxin. Antidiarrheals will be allowed at the discretion of the investigator, with the exception of BA sequestrants.

6 INVESTIGATIONAL PRODUCT

6.1 Identity of Investigational Product

The test product is volixibat potassium (volixibat), which will be provided in 5, 10 and 20 mg capsule form. Additional information is provided in the current Volixibat Potassium (SHP626) Investigator's Brochure.

The reference/comparator product is an identical PBO which will be provided in capsule form.

6.1.1 Blinding the Treatment Assignment

The IP will be supplied as double-blind blister packs. The actual double-blind treatment given to individual subjects is determined by a randomization schedule which will be automatically assigned by the interactive response technology (IRT). Placebo capsules, which exactly match the IP, will be used in the blister packs to provide the same number and size capsules for each of the doses within the treatment groups.

6.2 Administration of Investigational Product(s)

All IP and supplies will be provided by Shire or its designee. At each visit, subjects will be supplied with enough IP to last until the subsequent visit. Lost or damaged IP will be replaced as needed. Volixibat will be supplied to the clinical research center (CRC) as powder in capsule. Volixibat will be supplied in identical capsules in strengths of 5, 10, and 20 mg (with matched PBO).

6.2.1 Interactive Response Technology for Investigational Product Management

IRT will be used for the following investigational tasks:

- Randomization
- Supply management
- Inventory management and supply ordering
- Expiration tracking
- Returns
- Emergency unblinding

6.2.2 Allocation of Subjects to Treatment

This is a double-blind, PBO-controlled study. The actual treatment given to individual subjects is determined by a randomization schedule.

Subject numbers are assigned to all subjects as they consent to take part in the study. Within each site (numbered uniquely within a protocol), the subject number is assigned to subjects according to the sequence of presentation for study participation.

The randomization number represents a unique number corresponding to the IP allocated to the subject, once eligibility has been determined.

Individual subject treatment is automatically assigned by the IRT.

Once a randomization number/unique identifier has been assigned, that number must not be used again if, for example, a subject is withdrawn from the study. If a randomization number/unique identifier is allocated incorrectly, the clinical research associate (CRA)/study monitor must be notified as soon as the error is discovered.

IP packaging identification numbers, separate from randomization numbers/unique identifiers, may also be assigned to subjects for specific treatment assignment as dictated by the study. In these cases, the same IP packing identification number may not be assigned to more than 1 subject.

Subjects will be equally allocated to all volixibat doses and PBO if their randomization precedes the 24 week IA. If a subject's randomization occurs after the 24 week IA, subjects will be equally allocated to all remaining volixibat doses (determined based on the results of the IA) and PBO. The randomization will be stratified by baseline T2DM and NAS ≥ 6 or NAS = {4,5}. Subjects with fibrosis stages F0 through F3 may be enrolled, but the number of F0 subjects will be capped at 88 if 1 dose is dropped after the IA and at 78 if 2 doses are dropped (approximately 30% of the total number of subjects randomized).

6.2.3 Dosing

All doses of volixibat or matching PBO will be administered orally as a capsule in a double-blinded fashion. The first dose of IP for each subject will be administered in the clinic. The dose will be administered with 240 mL of water and should be given 30 minutes prior to the first meal of the day containing approximately 10-20 grams of fat. The subject should make all attempts to consistently take the IP around the same time each day. If a dose is missed at the normally scheduled time, the subject can make up the dose that day as long as no more than 1 dose is taken in a 10-hour period.

6.2.4 Unblinding the Treatment Assignment

The treatment assignment must not be broken during the study except in emergency situations where the identification of the IP is required for further treatment of the subject. The investigator should contact the CRO medical monitor and the Shire study physician at the same time and as soon as possible after the investigator has been unblinded.

In the event that the treatment assignment is broken, the date and the signature of the person who broke the code are to be recorded in the source documents and the IRT, and the reason for breaking the code will be recorded in the source documents and the clinical database. Upon breaking the blind, the subject is withdrawn from the study, but should be followed up for safety purposes. Any code-breaks that occur must be reported to the CRO medical monitor. Code-break information is held by the pharmacist/designated person at the site and by the CRO medical monitor for the study or designee.

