9.8.1 Primary Efficacy Endpoint

The primary endpoint is the binary response indicating (yes/no) whether a subject responded at Week 48 with a reduction of at least 2 points, without worsening of fibrosis, from baseline NAS.

The FAS will be used to assess the primary efficacy endpoint. The proportion of subjects at Week 48 with a reduction of at least 2 points without worsening of fibrosis from baseline NAS

will be analyzed. The difference between a volixibat dose and PBO will be tested with a stratified Cochran-Mantel-Haenzel test. The test will be stratified by presence or absence of T2DM at baseline and baseline NAS separated into two groups (NAS={4,5} or NAS={6,7,8}). Subjects with missing data for the primary efficacy endpoint at the Week 48 visit will be considered as non-responders. Holm multiplicity adjustment will be applied prior to determining statistical significance at the 0.1 level.

Analyses which explore the impact of the missing data on the primary efficacy endpoint will be conducted. These analyses may compare imputations of the missing values which favor the PBO and/or imputations which favor the active. In addition, analyses utilizing existing HFF and/or ALT data may be performed. Further, if the pattern of missing values does not appear uniformly distributed among the treatment arms, imputation method(s) based on informative missingness may also be performed. Analyses investigating the impact of missing data will be detailed in the Statistical Analysis Plan.

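### Section 6.2.4 ends study participation after any code break, so a subject unblinded before Week 44 who could have reached Week 48 will usually be counted as a non-responder without a biopsy

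*Protocol*

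**What the plan says.** Section 6.2.4 gives one ground for breaking the code: "The treatment assignment must not be broken during the study except in emergency situations where the identification of the IP is required for further treatment". The consequence follows in the same section: "Upon breaking the blind, the subject is withdrawn from the study, but should be followed up for safety purposes". No exception is listed, and nothing is said about efficacy assessments after the break.

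Section 4.5 covers discontinuation of IP for any reason. The Visit 9/end-of-study (EOS) and Visit 10 evaluations "are to be performed as completely as possible; however, the EOS liver biopsy will not be required for patients discontinuing prior to Week 44". Section 7.1.3 repeats the Week 44 waiver.

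Section 9.8.1 sets the primary analysis rule: "Subjects with missing data for the primary efficacy endpoint at the Week 48 visit will be considered as non-responders". It also promises sensitivity work: "Analyses which explore the impact of the missing data on the primary efficacy endpoint will be conducted".

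Histology is read centrally. The Synopsis names one central hepatopathologist, and Section 7.1.3 gives the central reader the final Week 48 assessment.

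Section 4.5.4 provides for an urgent safety review after a related death or two similar related serious adverse events. It adds: "The GDS TA Head, not the GSL involved in the study, may be unblinded as part of this urgent safety review, if required". It does not refer to 6.2.4 or say what then happens to the subject.

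**The concern.** The decision that a subject leaves the study is tied to who knows the treatment arm. It is not tied to whether the outcome can still be observed. The primary endpoint is a centrally read biopsy, so an unblinded site is a much weaker reason to stop observing than it would be for a site-rated or patient-reported outcome. The rule turns an outcome that could have been observed into a missing one, and the primary analysis then turns the missing one into a failure.

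The affected subjects generally remain in the denominator. The full analysis set needs only one post-baseline efficacy assessment, and liver biochemistry from Week 2 onwards qualifies. At stake is a small, avoidable loss of primary-endpoint data, which would bias the comparison if code breaks were unequal between arms.

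There is also a loose end in the text. Section 6.2.4 does not say how its withdrawal fits with the EOS evaluations in 4.5, or whether the restricted unblinding in 4.5.4 counts as a code break.

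**Working it through.** **1. Who is affected.** Reading 6.2.4, 4.5, 7.1.3 and 9.8.1 together:

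| Situation | Week 48 histology under the present text | Does 6.2.4 change the result? |
|---|---|---|
| Code broken before Week 44; subject would otherwise have continued to Week 48 | Withdrawn; biopsy not required; usually missing, so non-responder | Yes |
| Code broken before Week 44; IP would have stopped before Week 44 anyway | Biopsy already not required under 4.5 and 7.1.3 | Little or not at all |
| Code broken at or after Week 44 | 4.5 still calls for the EOS biopsy | Only if withdrawal is taken to override 4.5 |
| Related death | Normally absent whatever is done about the blind | No |
| Only the sponsor safety role unblinded under 4.5.4 | Not stated | Only on a literal reading of 6.2.4 |

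The first row carries the point.

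**2. The plan's own figure.** Inputs from Section 9.6 are 21% and 45% response, 80% power and 10% type I error with Holm. With two continued doses the first Holm step is 0.10/2 = 0.05, two-sided (Section 9.8).

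Uncorrected n = [1.960·√(2·0.33·0.67) + 0.842·√(0.21·0.79 + 0.45·0.55)]² / 0.24² = (1.303 + 0.541)² / 0.0576 ≈ 59.1, so 60 per group.

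With continuity correction, n = (59.1/4)·[1 + √(1 + 4/(59.1·0.24))]² ≈ 67.1, so 68 when rounded up, against the stated 67. Fisher's exact test at 67 per group has power 80.8%. The plan's figure is reproduced.

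**3. Effect per subject.** With 81 randomized per continuing arm, one lost responder moves the arm's rate by 1/81 = 1.23 points. With k code breaks and a 45% chance of response, the expected loss is 0.45·k/81:
- k = 1: 0.56 points
- k = 3: 1.67 points

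Both are set against a planned difference of 45 − 21 = 24 points. The values of k are assumptions.

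These are upper figures for that k. If only a share s of code-broken subjects would otherwise have reached a Week 48 biopsy, the loss is s times as large. For an illustrative s = 0.5 it is 0.28 to 0.83 points. The documents give neither k nor s.

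**4. Effect on power.** Let q be the share of an arm's outcomes that are converted to non-response, so that the response rate becomes p(1 − q). Power is for 67 per group at two-sided 0.05, uncorrected:

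| q (assumed) | Both arms equally | Active arm only |
|---|---|---|
| 0 | 84.8% | 84.8% |
| 1% | 84.3% | 83.5% |
| 3% | 83.1% | 80.8% |
| 5% | 81.9% | 77.7% |

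For reference, 1 to 3 subjects of 81 is 1.2% to 3.7%. The active-only column is a worst case; nothing in the protocol shows that code breaks would fall only there.

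**The case against.** The strongest reply is that withdrawal with safety follow-up after an emergency code break is a legitimate design choice, and that the protocol already limits the damage. Section 4.5 asks for the EOS evaluations whatever the reason for stopping IP. The biopsy before Week 44 is not required, but it is not forbidden. Section 9.8.1 commits to missing-data analyses, including methods for informative missingness if the pattern differs by arm. Many subjects with an emergency would stop IP early and lose the biopsy under 4.5 in any case. All of this stands, and it is why the effect is small. It does not remove the point: sensitivity analyses show the influence of lost histology but do not recover it, and 6.2.4 itself asks for nothing beyond safety follow-up.

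Three stronger readings are tempting, and the documents do not support them.

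- *Subjects with safety events are made non-responders by rule.* Section 6.2.4 applies only where the code is broken. Non-response comes from 9.8.1, and only when Week 48 histology is missing.
- *Safety observation ends early.* Section 6.2.4 keeps safety follow-up, and Section 8.1 follows adverse events to closure whether or not the subject is still in the study.
- *Section 4.5.4 permits what 6.2.4 forbids and so forces subjects out.* Taken literally, the urgent review lies outside the one ground in 6.2.4. But 6.2.4 is written around site code breaks: the investigator being unblinded, a signature in source documents, and code information held at the site and by the medical monitor. Section 4.5.4 is a narrow provision for one role outside the study. Section 9.5.1 has subjects continue after an unblinded interim comparison unless their dose is found unsafe, so the protocol does not treat every unblinding as a reason to withdraw. What is missing is mainly a cross-reference.

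**Conclusion.** The point holds in a limited form. For a subject whose code is broken before Week 44 and who might otherwise have stayed to Week 48, the withdrawal rule will usually replace a centrally readable outcome with an imputed failure. This is a stated rule and not a detail left open.

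The size is probably small: at most about 0.6 to 1.7 points of the 24-point planned difference for an assumed 1 to 3 code breaks in an active arm of 81. That range also assumes that every such subject would have had a Week 48 biopsy and would have responded at 45%, the active-arm rate of the cited trial. Both assumptions push the figure up. No material effect on the primary result is shown. A reader might infer that the losses would cluster in the active arms; 6.2.4 sets no condition about relatedness to drug, so that remains conjecture. This is a low-cost improvement and not a defect that threatens the trial.

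**What to change.** In Section 6.2.4, state that a code break does not by itself end study participation for outcome assessment. The subject stays for the scheduled efficacy and safety assessments, including the Week 48 biopsy where 4.5 and 7.1.3 already call for it. Leave decisions on IP to the existing sections.

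Reconcile 6.2.4 with the EOS evaluations and Week 44 waiver in 4.5 and 7.1.3, so that the three sections give one instruction. Add a cross-reference between 4.5.4 and 6.2.4: unblinding confined to the sponsor safety role, or to the DMC and its statistician, is not a code break under 6.2.4 and does not trigger withdrawal.

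The cost is a few sentences in 6.2.4 and matching references in 4.5, 4.5.4 and 7.1.3. No biopsy is added beyond those the protocol already requires. The downside is that a few subjects continue with the site knowing the arm, which could affect concomitant care or willingness to have the biopsy even though the reading is central. Flag these subjects for a sensitivity analysis.

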6.3 Labeling, Packaging, Storage, and Handling

6.3.1 Labeling

Labels containing study information and pack identification are applied to the IP container.

All IP is labeled with a minimum of the protocol number, medication identification number, dosage form (including product name and quantity in pack), directions for use, storage conditions, expiry date (if applicable), batch number and/or packaging reference, the statements 'For clinical trial use only', and/or 'CAUTION: New Drug - Limited by Federal (or USA) Law to Investigational Use', 'Keep out of reach of children', and the sponsor's name and address. Any additional labeling requirements for participating countries will also be included on the label.

Additional labels may, on a case-by-case basis, be applied to the IP in order to satisfy local or institutional requirements, but must not:

- Contradict the clinical study label
- Obscure the clinical study label
- Identify the study subject by name.

Additional labels may not be added without the sponsor's prior full agreement.

